1.2.2 Trametinib (Mekinist®)

Trametinib is absorbed orally with median time to achieve peak concentrations (t_{max}) of 1.5 hours post-dose. The mean absolute bioavailability of a single 2 mg tablet dose is 72%. The increase in exposure (C_{max} and AUC) was dose proportional following repeat dosing. Trametinib accumulates with repeat daily dosing with a mean accumulation ratio of 6.0 following a 2 mg once daily dose. Mean terminal half-life is 127 hours (5.3 days) after single oral dose administration. Steady-state was achieved by Day 15. *In vitro* and *in vivo* studies demonstrated that trametinib is metabolized predominantly via deacetylation alone or in combination with mono-oxygenation. The deacetylated metabolite was further metabolized by glucuronidation. The deacetylation is mediated by the carboxyl -esterases 1b, 1c and 2, with possible contributions by other hydrolytic enzymes. Drug-related material was excreted predominantly in the feces ($\geq 81\%$ of recovered radioactivity) and to a small extent in urine ($\leq 19\%$). Less than 0.1% of the excreted dose was recovered in urine.

1.3 Preclinical Data

1.3.1 CDX-3379 - Summary of Nonclinical Experience

CDX-3379 has shown the following activity in nonclinical studies as summarized in greater detail in the CDX-3379 investigator brochure:

- In vivo antitumor activity in ligand-independent xenograft models in which the tumor is driven by HER2. High levels of heterodimerization partners of ErbB3 through amplification or mutation (such as EGFR or HER2) may drive tumor growth without involvement of NRG
- Significant in vivo antitumor activity in ligand-dependent xenograft models in which an autocrine loop drives growth (tumor provides NRG and ErbB3) including models of HNSCC, squamous NSCLC and BRAF mutated tumors. Evaluation of human tumors indicates that the highest prevalence of NRG is observed in squamous tumors such as HNSCC, NSCLC and esophageal as well as BRAF mutated thyroid samples. Analysis of human HNSCC tumors indicates NRG is expressed broadly and independent of anatomical site and expressed in both HPV positive and negative tumors, although NRG levels are higher in HPV negative tumors.
- Significant in vivo antitumor activity including tumor regression when given in combination with agents that target other ErbB family members (in combination with cetuximab, which inhibits EGFR, in combination with afatinib, which inhibits EGFR, and in combination with trastuzumab, which inhibits HER2).

CONFIDENTIAL

- Increased expression of ErbB3 and sensitivity to NRG stimulation in response to BRAF mutated cells after treatment with BRAF inhibitors or MEK inhibitors. Combination treatment of tumor bearing mice with CDX-3379 with either a MEK inhibitor, a BRAF inhibitor, or their combination did not enhance antitumor activity in BRAF mutated tumor models that lack NRG expression, but resulted in enhanced antitumor activity in tumor models which express NRG.

To obtain sufficient nonclinical data on the safety and efficacy of CDX-3379 to support use in clinical trials and approval to market, the nonclinical testing program was designed to address efficacy and safety. The mouse and cynomolgus monkey were selected as pharmacologically relevant species for evaluation of safety of CDX-3379 based on sequence homology of ErbB3, affinity for binding of CDX-3379 to ErbB3, and comparable in vitro functional activity (ability to block NRG-induced ErbB3 phosphorylation).

CDX-3379 overall exhibited non-linear PK. Following the intravenous (IV) bolus administration of CDX-3379, exposure (area under the concentration time curve; AUC) increased in a greater than dose-proportional manner and clearance of CDX-3379 decreased from 96.0 to 49.9 milliliters (mL)/day/kilogram (kg) as the dose increased from 10 to 150 mg/kg twice weekly in mice, 41.0 to 5.74 mL/day/kg as the dose increased from 0.3 (single dose) to 150 mg/kg (weekly dose) in cynomolgus monkeys. There was moderate accumulation of CDX-3379 in mice and cynomolgus monkeys after repeat IV administrations. The accumulation ratio (AR) ranged from 1.2 to 2.3 for mice (twice weekly dosing), and 1.1 to 3.5 for cynomolgus monkeys (weekly dosing). No differences in the pharmacokinetics (PK) were observed between male and female animals. The presence of antibodies against CDX-3379 (anti-drug antibodies, ADA) within the dosing phase appeared to reduce CDX-3379 exposure in some animals.

There were no observed adverse effects in cluster of differentiation 1 (CD-1) mice or cynomolgus monkeys that were attributed to repeated IV administration of up to 150 mg/kg/dose of CDX-3379, the highest dose tested. In the Good Laboratory Practice (GLP) CD-1 mouse study, 8 toxicity animals and 14 toxicokinetic (TK) animals administered CDX-3379 died or were euthanized in moribund condition; however, the effects were not considered directly related to CDX-3379, but were attributed to anaphylactoid reactions from repeated exposure to a foreign antigen (because CDX-3379 is a human IgG1). In cynomolgus monkeys, there were also no CDX-3379-related effects on safety pharmacology parameters including behavior (as assessed by standard clinical observations), heart rate, body temperature, blood pressure, or electrocardiogram (ECG) measurements in cynomolgus monkeys. There were no adverse effects on local tolerance following IV bolus or infusion administration of CDX-3379 to CD-1 mice or cynomolgus monkeys.

1.3.2 Trametinib (Mekinist®) – Summary of Nonclinical Experience

See IB for detailed information

1.4 Clinical Data to Date

1.4.1 CDX-3379 - Summary of Clinical Experience

The clinical experience with CDX-3379 has included three clinical studies.

Study KTN3379-CL-001 was a first-in-human Phase 1/1b study of adult patients with advanced solid tumors refractory to standard therapy (or for which no standard therapy existed). Patients received a 60-minute IV infusion of CDX-3379 once every three weeks as monotherapy (Phase 1) or in combination with other targeted anticancer agents (Phase 1b). In the Phase 1 study portion, a total of 21 patients were treated across three dose-escalation cohorts (5, 10, and 20 mg/kg), an intermediate-dose level cohort (15 mg/kg), and a flat-dose cohort (1200 mg). As no dose limiting toxicities were reported, a maximum tolerated dose for CDX-3379 monotherapy was not determined. Pharmacokinetic (PK) analysis showed trough CDX-3379 plasma levels exceeding target concentrations at doses ≥ 10 mg/kg. During this portion of the study, plasma ErbB3 levels increased in all patients at all doses consistent with target engagement; however, no objective tumor responses were reported.

CONFIDENTIAL

1.4.2 Trametinib (Mekinist) - Summary of Clinical Experience

Phase II dosing of trametinib was determined to be 2 mg once a day based on the phase I dose-escalation trial ^{7,44} of 206 advanced solid tumor patients which included 97 patients with both *BRAF* mutant and wild type melanoma. The loading dose of trametinib at 10mg daily for two days followed by 3 mg daily thereafter exceeded the maximum tolerated dose, with dose-limiting toxicities including rash, diarrhea, and retinopathy. Trametinib 3 mg daily was deemed to be the maximum tolerated dose and after the first cycle, 1 patient discontinued therapy due to fatigue, 5 patients required dose interruptions, and 2 patients required dose-reduction. Pharmacodynamic testing of trametinib 2 mg once daily in *BRAF* mutant patients showed a 62% inhibition of pERK, 83% inhibition of Ki67, and 171% increase of p27, which were improved from the pre-clinical target thresholds ⁴⁴. Trametinib produced a response rate of 33% in the 30 *BRAF* mutant patients including 2 complete responses and 5 partial responses among the 16 patients on a dose of 2 mg once daily. Treatment-related adverse events included acneiform dermatitis or rash, (82%), diarrhea (45%), peripheral edema (35%),

CONFIDENTIAL

fatigue (35%), nausea (12%), ocular events (10%) (which occurred mostly at doses greater than 2 mg daily), and a decrease in ejection fraction (7%) 7.

See IB for further detailed information

1.5 Dose Rationale

Participants on this clinical trial will receive CDX-3379 at 15mg/kg IV every three weeks and trametinib 2mg PO daily.

A single agent study evaluated CDX-3379 at a range of concentrations, with upper limit of 20mg/kg without observed dose limiting toxicity. Pharmacokinetic (PK) analysis showed trough CDX-3379 plasma levels exceeding target concentrations at doses ≥ 10 mg/kg. In combination studies of CDX-3379 with other monoclonal antibodies, a few patients experienced side effects at the 20mg/kg dosing, requiring decrease to 15mg/kg. CDX-3379 in combination with another oral TKI that disrupts the BRAF/MEK/ERK pathway (vemurafinib) was well tolerated with no reported DLTs with doses up to 20mg/kg. At 15mg/kg, objective tumor responses were observed.

The recommended dose of trametinib is 2mg daily. This dose was chosen based on a number of clinical trials as the recommended dosing, even though the maximum tolerated dose being 3 mg daily.

Given the cumulative information regarding dosing and observed response, the recommended starting doses for the combination of ERBB3 and trametinib were chosen to be CDX-3379 at 15mg/kg IV every three weeks and trametinib 2mg PO daily.

1.6 Research Risks & Benefits

1.6.1 Risk of Study Drug

1.6.1.1 CDX-3379

CDX-3379 has been given to approximately 80 patients with different types of advanced cancers in three clinical studies. More than half of these patients have received CDX-3379 in combination with another anticancer treatment. The patients who received CDX-3379 in combination with other anticancer medications, including cetuximab, tended to experience more frequent and more severe side effects.

Overall, side effects thought to be related to study treatment have included the following:

- Frequent side effects (occurring in $>20\%$ of the patients):
 - Diarrhea (54%; *diarrhea*)
 - Nausea (27%; *nausea*)
 - Fatigue (28%; *fatigue*)
 - Rash (21%; *Rash, Rash erythematous, Rash macular, Rash maculo-papular, Rash popular, Rash pruritic*)
- Somewhat frequent side effects (occurring in 11-20% of the patients):
 - Mucositis/Stomatitis (painful inflammation and ulceration of the mucous membranes lining the mouth or digestive tract) (16%; *Mucosal inflammation, Stomatitis*)
 - Vomiting (15%; *vomiting*)
 - Low blood potassium (15%, *Hypokalaemia, Blood potassium decreased*)

CONFIDENTIAL

- Decreased appetite (12%; *Decreased appetite*)
- Less frequent side effects (occurring in 6-10% of the patients):
 - Bad taste in the mouth (10%; *Dysgeusia*)
 - “Pimply” (or acne-like) rash (10%; *Dermatitis acneiform*)
 - Weight loss (9%; *Weight decreased*)
 - Low blood magnesium (9%; *Hypomagnesaemia, Blood magnesium decreased*)
 - Dehydration (7%; *Dehydration*)
 - Itching (7%; *Pruritus*)
 - Weakness (6%; *Asthenia*)
 - Dizziness (6%; *Dizziness*)
 - Dry skin (6%; *Dry skin*)

Some of the above events required hospitalization or were otherwise considered serious.

The adverse drug reactions (ADRs; expected adverse events) listed were identified by the Sponsor based on reasonable evidence of casual association with CDX- 3379, based on clinical experience as of May 24, 2017. The Sponsor consults this section as reference for expectedness of SAEs with regard to expedited reporting requirements for regulatory purposes. A SAE will be considered “unexpected” if not consistent in nature or severity with the listed ADRs, with consideration to the noted serious adverse drug reactions (SARs; treatment related SAEs recorded per CTCAE v4.03 criteria). The table of ADRs is not a complete list of adverse events reported in clinical trials. A cumulative tabulation of all adverse events assessed as treatment-related by the investigators across all Celldex-sponsored studies of CDX-3379 are provided in the IB.

1.6.1.1.1 Management of Toxicity Related to CDX-3379

Potential toxicity and guidance for the management of toxicity is summarized below. However, the CDX-3379 Investigator’s Brochure is the Single Reference Safety Document that provides complete and relevant information about the known safety profile of CDX-3379. Updates to these data will be provided as revisions to the Investigator’s Brochures and through Investigational New Drug (IND) Safety Reports submitted to the investigator by Celldex, rather than by amendment to this section of the protocol.

CDX-3379 alone has been well tolerated with mild to moderate adverse events including diarrhea, rash, mucositis, fatigue and dry mouth and severe toxicity (diarrhea, hypokalemia) reported in only two of 21 patients. Most common adverse events reported in the Phase 1b study for the combination of CDX-3379 and targeted agents (including other EGFR or BRAF inhibitors) have included diarrhea, mucositis and rash with diarrhea and mucositis meeting criteria for DLTs.

As a routine precaution, the investigative site’s medical staff is to closely observe patients for the duration of the CDX-3379 infusion and for at least 1 hour after the end of the infusion, in an area with resuscitation equipment and agents used for management of infusion related reactions (e.g., antihistamines, epinephrine, corticosteroids). A nurse must be present in the immediate treatment area throughout the infusion and observation period. A physician must be in close proximity to the patient treatment area.

In order to mitigate the risk and severity of adverse events resulting from study therapy, patients will undergo extensive monitoring throughout the study and guidelines will be implemented per this protocol to ensure that study therapy is discontinued and/or modified as necessary and medical therapy is instituted when appropriate to manage adverse events.

Dermatologic Toxicity

Dermatologic toxicities have been reported with CDX-3379 as single agent in the Phase 1 trial in advanced cancer patients, and have also been reported in study [KTN3379-CL-001](#) amongst patients treated with the

CONFIDENTIAL

combinations containing CDX-3379. Supportive management with topical, oral antibiotic therapy or other measures should be taken according to institutional standards.
Recommended dose modification for grade 3 or 4 acneiform rash is provided in Table 5.

Table 5. Dose Modification Guidance for Rash

	CDX-3379
1 st Occurrence	Delay infusion by 1-2 weeks · Improvement: Resume at same dose · No Improvement: Discontinue
2 nd Occurrence	Delay infusion by 1-2 weeks · Improvement: Resume at same dose · No Improvement: Discontinue
3 rd Occurrence	Delay infusion by 1-2 weeks · Improvement: Reduce dose by one level · No Improvement: Discontinue
4 th Occurrence	Delay infusion by 1-2 weeks · Improvement: Reduce dose by one level · No Improvement: Discontinue

Diarrhea

Diarrhea is a common toxicity associated with cancer treatments in general and occurs frequently with mAb and tyrosine kinase inhibitors that target the ErbB family of receptors ([Stein et al, 2010](#)). Specifically, diarrhea was reported in the Phase 1 study of CDX-3379 conducted in patients with advanced solid tumors and was also a frequent adverse event among patients treated with the combination of CDX-3379 and targeted agents.

Treatment guidelines exist for the management of cancer treatment-induced diarrhea that include, but are not limited to, the following key elements independent of dose modifications:

- Patient education
- Maintaining oral hydration
- Early intervention with and frequent use of anti-diarrheals until sustained resolution (eg., loperamide initial dose of 4 mg followed by 2 mg every 2 hours)
- Frequent monitoring and replacement of electrolytes (eg., potassium, magnesium)

Patients should be managed according to institutional standards and patients should be carefully instructed to monitor for diarrhea as well as be instructed on proper management of these symptoms as they occur or change during the course of study therapy.

Patients with grade 4 diarrhea should discontinue study therapies unless the toxicity resolves quickly and the patient is benefitting from therapy, in which case the therapy may be continued at a reduced dose after discussion with the Medical Monitor.

Recommended dose modification grade 2 or 3 diarrhea is provided in Table 6.

Table 6. Dose Modification Guidance for Diarrhea

Grade 3 or Persistent Grade 2 Diarrhea*	CDX-3379
--	-----------------

CONFIDENTIAL

1 st Occurrence	
 · Delay infusion by 1-2 weeks till diarrhea ≤ Grade 1 · Resume at same dose
2 nd Occurrence	
 · Delay infusion by 1-2 weeks till diarrhea ≤ Grade 1 · Reduce dose by one level
3 rd Occurrence	
 · Delay infusion by 1-2 weeks till diarrhea ≤ Grade 1 · Reduce dose by one level
Additional occurrence(s)	
 · Delay infusion by 1-2 weeks till diarrhea ≤ Grade 1 · Reduce dose by one level or discontinue

* Despite maximum medical therapy with anti-diarrheals. Persistent is defined as diarrhea that lasts ≥ 3 days.

Infusion Reactions

Infusion reactions, including those that are severe, are possible with CDX-3379. Infusion reactions may occur during the infusion of CDX-3379 or may be delayed until any time after the infusion.

For infusion-related reactions that occur during the administration of CDX-3379 consider temporarily or permanently discontinuing CDX-3379 depending on the severity of the infusion reaction and the required interventions. For NCI CTC Grade 1 or Grade 2 infusion reactions, the infusion may be resumed at a 50% reduction in rate after symptoms have resolved and may be considered for subsequent cycles. For Grade 1 or Grade 2 infusion reactions, patients will be treated with Benadryl and/or Soluortef for their first infusion related reaction. If patients experience an infusion related reaction, patients will be pre-medicated with Benadryl and/or Soluortef prior to their next infusion. The following infusion will resume at the full dose. If a second infusion related reaction occurs, subsequent infusions will be given at a 50% reduction. Immediately and permanently discontinue CDX-3370 for serious infusion reactions, requiring medical intervention and / or hospitalization.

Patients who develop a grade 3 or 4 infusion reaction during CDX-3379 should not receive further treatment with CDX-3379. Grade 3 or Grade 4 reactions will be treated with Benadryl, Soluortef and/or an H2 blocker.

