1.6.1.2.1 Management of Toxicity Related to Trametinib

CONFIDENTIAL

This material is the property of the NYU School of Medicine and Langone Medical Center. Do not disclose or use except as authorized in writing by the study sponsor

Table 1. Recommended Dose Modifications for Trametinib

Target Organ	Adverse Reaction^a	Dose Modification
Cutaneous	Grade 2 rash (tolerable)	Continue treatment and monitor
	Intolerable Grade 2 rash or Grade 3 or 4 rash	Withhold Trametinib for up to 3 weeks If improved within 3 weeks, resume Trametinib at a lower dose (reduced by 0.5 mg) or discontinue Trametinib in patients taking Trametinib 1 mg daily
	Intolerable Grade 2 or Grade 3 or 4 rash that does not improve within 3 weeks despite interruption of Trametinib dosing	Permanently discontinue Trametinib
Cardiac	Asymptomatic, absolute decrease in LVEF of 10% or greater from baseline and is below institutional lower limits of normal (LLN) from pretreatment value	Withhold Trametinib for up to 4 weeks. If improved within 4 weeks, resume Trametinib at a lower dose (reduced by 0.5 mg) or discontinue Trametinib in patients taking Trametinib 1 mg daily
	
 - Symptomatic congestive heart failure - Absolute decrease in LVEF of greater than 20% from baseline that is below LLN - Absolute decrease in LVEF of 10% or greater from baseline and is below LLN that does not improve to normal LVEF value within 4 weeks following interruption of Trametinib 	Permanently discontinue Trametinib
Ocular	Grade 2-3 retinal pigment epithelial detachments (RPED)	Withhold Trametinib for up to 3 weeks. If improved to ≤ Grade 1 within 3 weeks, resume Trametinib at a lower dose (reduced by 0.5 mg) or discontinue Trametinib in patients taking Trametinib 1 mg daily. If it does not improve to ≤ Grade 1 within 3 weeks, discontinue Trametinib.

CONFIDENTIAL

Ocular	Retinal Vein Occlusion	Permanently discontinue Trametinib
Pulmonary	Interstitial lung disease/pneumonitis	Permanently discontinue Trametinib
Other	Intolerable Grade 2 adverse reaction Grade 3 adverse reaction	Withhold Trametinib for up to 3 weeks. If Grade 3 adverse reaction improves to \leq Grade 1 following interruption of Trametinib within 3 weeks then reduce dose of Trametinib by 0.5mg or discontinue Trametinib in patients taking Trametinib 1 mg daily.

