	Grade 4 adverse reaction or Grade 3 adverse reaction that does not improve to Grade 0-1 within 3 weeks	Permanently discontinue Trametinib

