1.6.2 Overlapping Toxicities

Unless a side effect is specific to only trametinib (cardiac (red LVEF), ocular (RPED, RVO), and/or pneumonitis), both drugs should be held together. With the exception of the trametinib specific side effects, all other side effects can be considered from either medication.

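### Grade 4 diarrhea has two conflicting instructions for trametinib, and the reduction after a second infusion reaction does not say rate or dose

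*Combined protocol and SAP*

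**What the plan says.** **Grade 4 diarrhea.** The CDX-3379 guidance (Section 1.6.1.1.1) reads "Patients with grade 4 diarrhea should discontinue study therapies unless the toxicity resolves quickly" and the patient is benefitting, and continues "in which case the therapy may be continued at a reduced dose after discussion with the Medical Monitor". The trametinib guidance (Section 1.6.1.2.1, Table 1) has no diarrhea row. The last row, for other reactions, covers "Grade 4 adverse reaction or Grade 3 adverse reaction that does not improve to Grade 0-1 within 3 weeks", and its action is permanent discontinuation.

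**Infusion reaction.** For grade 1 or 2 reactions, Section 1.6.1.1.1 first allows the infusion to resume at half the rate. It then prescribes medication, says that the next infusion returns to the full dose, and adds: "If a second infusion related reaction occurs, subsequent infusions will be given at a 50% reduction". The same paragraph permanently stops the antibody for serious reactions that need medical intervention and/or hospital admission. The next paragraph stops it for grade 3 or 4.

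**Grade 3-4 acneiform rash.** CDX-3379 Table 5 says "Delay infusion by 1-2 weeks", then resume if improved or discontinue if not. Trametinib Table 1 says "Withhold Trametinib for up to 3 weeks", then resume 0.5 mg lower if improved.

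**Link between the drugs.** Section 1.6.2 says that "both drugs should be held together" unless the event is one of the listed trametinib-specific ones (cardiac, ocular, pneumonitis). All other side effects may be regarded as coming from either drug.

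**Where it is counted.** Section 1.6.3 makes permanent discontinuation of either drug a DLT. It also makes nonhematologic toxicity of grade 3 or higher a DLT, with short exceptions. Section 3.1 pauses enrollment if at least 30% of patients discontinue for toxicity, with a hold after the first 20 patients.

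**The concern.** For grade 4 diarrhea that resolves quickly in a patient who is benefitting, one section permits continuing at a reduced dose and the other orders a permanent stop of trametinib. Attribution does not settle which applies, because Section 1.6.2 lets diarrhea be ascribed to either drug. For a second infusion reaction, the single instruction can be read as two different treatments. The line between a reaction that is medicated and continued and one that ends CDX-3379 is not clearly drawn.

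Two patients with the same event could therefore be managed differently. One could be counted as a discontinuation in the safety rule of Section 3.1 and the other not.

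**Working it through.** No figure in the plan depends on these rules, so there is none to reproduce. The check is mainly a comparison of texts.

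**1. Grade 4 diarrhea, trametinib**
- Section 1.6.1.1.1: the main clause concerns the study therapies in the plural. The exception allows a reduced dose after discussion with the Medical Monitor.
- Table 1, last row: permanent discontinuation for any grade 4 reaction, without exception.
- Result: when the exception is used for trametinib, the two texts conflict.

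**2. Second infusion reaction**
- Read as dose: 15 × 0.5 = 7.5 mg/kg. The cohort table in Section 3.1 has 15, 10 and 5 mg/kg only.
- Read as rate: 60 / 0.5 = 120 minutes, against the 60-minute infusion in Section 5.4.2.
- The sentence just before it speaks of dose. The only earlier 50% speaks of rate.

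**3. Rash windows.** Assume that the CDX-3379 delay runs from the due infusion and the trametinib hold from onset. For onset *d* days before the due infusion, the CDX-3379 decision falls *d* + 7 to *d* + 14 days after onset. The trametinib limit is 21 days.
- *d* = 0: CDX-3379 is decided at 7 to 14 days. A rash that improves only in week 3 stops CDX-3379 and resumes trametinib.
- *d* = 14 (onset on day 8, infusion due on day 22, delayed to day 29-36): CDX-3379 is decided at 21 to 28 days, so the windows meet at day 21 and CDX-3379 may run later.
- The latest dates coincide at *d* = 7, from *d* + 14 = 21.

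Whether the windows diverge thus depends on timing.

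**4. DLT count.** Section 1.6.3 excepts alopecia, grade 3 nausea, vomiting or diarrhea under 72 hours, and brief asymptomatic grade 3 electrolyte changes. Grade 4 diarrhea and grade 3-4 rash are not excepted. They are DLTs by grade whichever modification text is followed, so the 2-of-6 rule is unaffected by them. A grade 1-2 infusion reaction is a DLT only if it is read as requiring a permanent stop.

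**5. How much one patient can matter.** The documents give no rates for the disputed events, so *p* below is an assumed rate per patient (exact binomial, independent patients).
- DLT rule: P(X ≥ 2 of 6) = 1 − (1−p)^6 − 6p(1−p)^5. If one patient is already counted: P(X ≥ 1 of 5) = 1 − (1−p)^5.
- Discontinuation rule: 0.30 × 20 = 6 patients, so P(X ≥ 6 of 20). If one patient is already counted: P(X ≥ 5 of 19).

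| Assumed p | ≥2 of 6 | ≥1 of 5 | ≥6 of 20 | ≥5 of 19 |
|---|---|---|---|---|
| 10% | 0.11 | 0.41 | 0.01 | 0.04 |
| 20% | 0.34 | 0.67 | 0.20 | 0.33 |
| 30% | 0.58 | 0.83 | 0.58 | 0.72 |

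The second and fourth probability columns are conditional on one patient having been reclassified. They do not say how likely that is. For the DLT rule they apply only to a lower-grade infusion reaction.

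**The case against.** The strongest defence is that each drug has its own guidance and that the diarrhea exception is narrow. It is a permission, it needs discussion with the Medical Monitor, and it sits in the CDX-3379 section. Its closing words turn to the singular, so it could be meant for CDX-3379 alone. On that reading the rules coexist. But the text does not say so, and the exception qualifies a clause about the study therapies together. The Medical Monitor step limits drift between sites, of which there is one and possibly a second, but it does not remove the conflict.

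On infusion reactions, the defence is largely right about type: this is one missing word in guidance for one drug, not two opposed rules. The word serious also does some work in separating reactions that end treatment. But it is tied to needing medical intervention, and grade 1-2 reactions are themselves medicated.

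Three stronger readings are tempting, and the documents do not support them.
- **That the DLT count for grade 4 diarrhea or rash turns on which text is followed.** It does not: Section 1.6.3 counts both by grade.
- **That the two rash tables contradict each other outright.** They govern different drugs, and different resumption steps are compatible. The joint hold is worded as a recommendation and covers holding only, not dose steps or permanent stopping.
- **That the reported side-effect rates size the problem.** Diarrhea (54% with CDX-3379, 45% with trametinib) and rash (21% and 82%) are not tied to the grades in dispute. The CDX-3379 figures pool about 80 patients, more than half on combinations. The 82% includes acneiform dermatitis; the 21% does not, since that is listed separately at 10%. For CDX-3379 alone, Section 1.6.1.1.1 reports severe toxicity in two of 21 patients.

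**Conclusion.** The point holds in limited form. For trametinib after grade 4 diarrhea, the two instructions conflict on their plain wording. The reduction after a second infusion reaction is undefined, and the boundary for permanent stopping after an infusion reaction is unclear. The rash windows are a lesser matter that depends on when the rash starts.

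The consequence falls on consistent patient management and the 30% discontinuation rule, and on the DLT count only for lower-grade infusion reactions. At an assumed 20% discontinuation rate, one patient already counted moves the chance of reaching 6 of 20 from 0.20 to 0.33. This treats stopping one drug as discontinuing treatment, which Section 3.1 does not state. Reaching the threshold leads to a pause and an assessment, not to automatic closure. How often the disputed events occur cannot be derived from the documents. The conflict should be corrected, but it does not undermine the design.

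**What to change.** The sponsor should reconcile Section 1.6.1.1.1 with Sections 1.6.1.2.1 and 1.6.2, and:

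- give grade 4 diarrhea one consistent instruction for each drug;
- state whether the 50% reduction after a second infusion reaction is in rate or dose;
- clarify which infusion reactions lead to permanent stopping, given that grade 1-2 reactions are also medicated;
- state how the two rash windows work under the joint hold, including the day from which each is counted;
- say in Section 3.1 whether stopping only one drug counts toward the 30% rule.

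Which clinical rule applies is for the sponsor to decide. The cost is a few text edits. Sample size and analysis do not change.
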